8.4.2 Packaging, labeling, and storage

The packaging and labeling of IMP will be performed under the responsibility of the Department of Pharmaceutical Development, A. Menarini Research & Business Service GmbH, [name], [name].

The febuxostat film coated tablets (20 mg) are packed in blisters consisting of a laminated aluminium foil (OPA 25 µm / Al 45 µm / PVC 60 µm) sealed with rigid aluminium foil (20 µm hard aluminium foil with heat seal lacquer), synonym: Al-Al blisters.

The febuxostat film coated tablets (80 mg and 120 mg) are packed in blisters consisting of a PCTFE (polychlorotrifluoroethylene) / PVC based film lamination (ACLAR RX-160 15 µm / PVC 250 µm) sealed with a 20 µm lacquered push through aluminium foil.

The IMP will be provided in treatment boxes (blister cards) to be dispensed starting from Visit 1 (Day 1). The blisters (primary packaging) will be permanently fixed in blister cards (secondary packaging).

For the 40 mg dose cohort, the blister cards will contain 28 febuxostat film coated tablets (20 mg) (2 tablets of 20 mg daily intake, medication for 14 days incl. surplus).

For the 60 mg dose cohort, the blister cards will contain 42 febuxostat film coated tablets (20 mg) (3 tablets of 20 mg daily intake, medication for 14 days incl. surplus).

For the 80 mg dose cohort, the blister cards will contain 14 febuxostat film coated tablets (80 mg) (1 tablet of 80 mg daily intake, medication for 14 days incl. surplus).

For the 120 mg dose cohort and adult treatment group, the blister cards will contain 14 febuxostat film coated tablets (120 mg) (1 tablet of 120 mg daily intake, medication for 14 days incl. surplus).

Labeling: the IMP will be labeled in compliance with the current valid international and corresponding national requirements. The treatment box (blister card) labels will have a peel-off section which has to be attached to the corresponding section in the drug accountability log upon dispensing of the IMP. The peel-off part reports the treatment box number to identify the treatment as assigned through IxRS. The fixed section of the label will report the contents of the treatment box and the instructions how to administer and store the IMP.

Storage: at the study site, the IMP has to be stored at controlled room temperature. The following storage recommendations are in place: “Do not store below 15°C and above 25 °C” and “Store in the original package”. The IMP must be kept in a secure area, out of reach of children and inaccessible to unauthorized individuals.

8.4.3 Drug accountability

Upon receipt of all IMP, study site personnel will open the shipment package, verify the contents as stated on the enclosed shipping form, and confirm the receipt through IxRS.

The IxRS will be used to record the IMP delivery to the study site, the inventory at the site, the use by each patient, including dates, quantities, batch/serial numbers, expiry dates, and the unique code numbers assigned to the IMP (treatment box number) and patients (patient number).

The Investigator will be responsible for documenting the dispensing of the IMP to the patient by entering the treatment box number in the source document and in the eCRF when the treatment is administered to in- as well as out-patient regimen. Furthermore, the number of tablets dispensed and any used/unused IMP will be recorded by the Investigator in the study specific drug accountability form.

8.4.4 Destruction of surplus medication

At the end of the study, all remaining IMP will be reconciled under the responsibility of the Investigator at the site. The IMP will be subsequently returned to the Department of Pharmaceutical Development, A. Menarini Research & Business Service GmbH or appointed depots.

8.5 TREATMENTS

8.5.1 Treatment Allocation

The study will be performed according to an open design; no blinding technique will be adopted.

Eligible patients will receive study treatment at Visit 1 (Day 1) after completing the relevant “prior to drug administration” procedures and re-checking of the eligibility criteria.

The IMP box assignment will be performed by means of the IxRS system (see section 10.1.2) without any randomized allocation. The first ≈24 children will be allocated to the 40 mg dose, the following ≈24 children to the 60 mg dose. The first ≈24 adolescents will be allocated to the 80 mg dose, the following ≈24 adolescents to the 120 mg dose. The ≈24 adults will be allocated to the 120 mg dose.

For children, the 20 mg febuxostat tablets will be used, whereas for adolescents and adults the market product ADENURIC® 80 mg and 120 mg will be employed as represented below:

Table 1. Febuxostat: Treatment dose and form

Patient Population	Treatment dose	Treatment form
Children	febuxostat 40 mg	2 tablets 20 mg
	febuxostat 60 mg	3 tablets 20 mg
Adolescents	ADENURIC® 80 mg	1 tablet 80 mg

	ADENURIC® 120 mg	1 tablet 120 mg
Adults	ADENURIC® 120 mg	1 tablet 120 mg

8.5.2 Treatment administration - frequency and duration of application

Eligible patients will receive oral administration of the following dose of febuxostat per age group:

- Children

Cohort 1: 40 mg once daily;

Cohort 2: 60 mg once daily.

- Adolescents

Cohort 3: 80 mg once daily;

Cohort 4: 120 mg once daily.

- Adults

120 mg once daily.

Minimum treatment duration will be of 7 days starting from Visit 1 (Day 1), which shall occur 2 days prior to the planned start of first chemotherapy cycle. The Investigator will be given the possibility to prolong the treatment duration up to 9 days on the basis of the chemotherapy regimen administered to the patient.

8.5.3 Treatment compliance

The study treatment will be dispensed at each study visit starting from Visit 1 (Day 1) to Visit 7 (Day 7) at the site by the Investigator. The Investigator will be given the possibility to prolong treatment duration up to 9 days on the basis of the chemotherapy regimen chosen.

The Investigator will be responsible for documenting the dispensation of the IMP to the patient by entering the treatment box number in the source document and in the eCRF when the treatment is administered to in- as well as out-patients. Furthermore, the number of tablets dispensed and any used/unused IMP will be recorded by the Investigator in the study specific drug accountability form, including dates, quantities, batch/serial numbers, expiry dates, and the unique code numbers assigned to the IMP (treatment number) and patients (patient number).

8.5.4 Dosage modification

No dose adjustment is allowed.

8.5.5 Concomitant Medication

Patients are not allowed to receive:

- any other investigational agent
- any other hypouricemic agent, such as allopurinol, rasburicase or probenecid;
- mercaptopurine/azathioprine.

In case of concomitant use of theophylline in patients receiving febuxostat 120 mg strength, a careful monitoring is recommended during the treatment period. In particular, theophylline blood levels have to be controlled.

Concomitant and prior (i.e. within 30 day before Visit 1, Day 1) medications shall be carefully checked because the use of the above reported medications may represent an exclusion criterion to make the patient eligible to participate in the study and to receive the study treatment. Furthermore, the regular and occasional use of any concomitant medication has to be recorded starting from Screening Visit until the final Follow Up/End of Study Visit (Visit 10, Day 14±2 days).

Patients have to receive adequate hydration: increased hydration ranging from 2 to 3 L/m² per day is recommended according to TLS management guidelines.

Concomitant and prior (i.e. within 30 day before Visit 1, Day 1) medications will be recorded in eCRF.

8.6 STUDY PROCEDURES AND ASSESSMENTS

8.6.1 Study Schedule

A maximum of 11 study visits are scheduled including Screening, as depicted in the study flow chart (see section 2.1) and summarized below.

Starting from Start of Treatment (Visit 1, Day 1) to the Evaluation Visit (Visit 8, Day 8), site visits must be performed daily; an additional visit can be scheduled on Day 9 (Visit 9) for patients requiring 9 days of treatment, upon Investigator's decision to prolong the treatment duration. Visits may occur as in-hospital or as ambulatory visits, according to the local clinical practice.

The Follow up/End of Study Visit is scheduled at Day 14 (± 2 days).

The treatment period can last from 7 to 9 days, evaluated by the Investigator on the base of the chemotherapy regimen administered to the patient. All assessments that are relevant to the study endpoints will be collected during the treatment period (Day 1-Day 7) and at the Evaluation Visit (Visit 8, Day 8). Each patient will complete the study at the time of the Follow up/End of Study Visit (Visit 10, Day 14 ± 2 days).

A summary of the study assessments at each visit is specified below.

Written informed consent shall be provided by adult patients or by parents (one or both, according to local regulations) or by legal guardian for children and adolescents, PRIOR to start any study procedures.

8.6.1.1 Screening Visit (Day -9 to Day 1)

Potentially eligible patients with hematological malignancies scheduled for first cytotoxic chemotherapy cycle will undergo the following procedures:

- assessment of inclusion/exclusion criteria;
- demographic data collection;
- medical history;
- prior and concomitant medication;
- physical examination and vital signs (i.e. blood pressure [BP], heart rate [HR], breathing rate [BR], body temperature [T]);
- Karnofsky performance status (KPS) / Lansky Play performance status (LPS) evaluation;
- 12 Lead ECG;
- blood sampling and urine collection for safety laboratory tests, including pregnancy test (if applicable);
- record of adverse events.

NOTE-1: Study procedures under Screening Visit may occur also on more than one day.

NOTE-2: Results of safety laboratory tests (biochemistry, haematology, coagulation, urinalysis and pregnancy test, when appropriate) and ECG which have been performed in the context of the standard patient's management can be recorded in the e-CRF under Screening Visit procedures, provided that they have been done within 24 hours prior to the Screening Visit (Visit 1, Day 1).

NOTE-3: Re-screening is allowed but requires sponsor/medical monitor's approval. A patient may maximally be re-screened once.

8.6.1.2 Visit 1, Start of Treatment (Day 1)

Start of Treatment Visit will be performed 2 days prior to the scheduled chemotherapy. During the Start of Treatment Visit, the following procedures will be performed:

Prior to the drug administration:

- record of adverse events and change in concomitant medication;
- re-check of inclusion/exclusion criteria and patient's eligibility confirmation;
- physical examination and vital signs;
- KPS/LPS evaluation;
- blood sampling and urine collection for safety laboratory tests (**NOTE:** safety laboratory tests performed within 24 hours do not need to be repeated at Visit 1, Day 1);
- blood sampling for centralized laboratory test (sUA); whenever possible blood sampling for centralized laboratory test (sUA) will be collected in conjunction with safety laboratory tests to reduce the patient's discomfort of additional venopunctures;
- assessment of LTLS/CTLS;
- allocation of investigational medicinal product (IMP) treatment box as per IxRS assignment.

Study drug administration:

- administration of febuxostat as per age group.

After study drug administration:

- assessment of the age-appropriate formulation acceptability (only for children).

NOTE: Screening Visit and Visit 1 (Day 1) may occur on the same day. Common assessments will be performed only once.

8.6.1.3 Visit 2 (Day 2)

- record of adverse events and change in concomitant medications;
- vital signs;
- KPS/LPS evaluation;
- pre-dose PK blood sampling;
- blood sampling for safety laboratory test, including centralized laboratory test (sUA);
- study drug administration;
- assessment of the age-appropriate formulation acceptability (only for children).

8.6.1.4 Visit 3 (Day 3)

- record of adverse events and change in concomitant medications;
- vital signs;
- KPS/LPS evaluation;
- 12 Lead ECG;
- pre-dose PK blood sampling;
- blood sampling for safety laboratory test, including centralized laboratory test (sUA);
- study drug administration;
- assessment of the age-appropriate formulation acceptability (only for children);
- assessment of LTLS/CTLS;
- starting of chemotherapy regimen.

8.6.1.5 Visits 4-7 (Days 4-7)

On each day from Day 4 to Day 7, the following assessments will be performed:

- record of adverse events and change in concomitant medications;
- vital signs;
- KPS/LPS evaluation;
- pre-dose PK blood sampling;
- blood sampling for safety laboratory test, including centralized laboratory test (sUA);
- study drug administration;
- assessment of the age-appropriate formulation acceptability (only for children);
- 4 additional post-dose PK blood sampling ONLY at Day 7 (Visit 7) at the assigned sampling time intervals: 0.5-2 hours, 2-4 hours, 4-6 hours and 6-8 hours;
- urine collection for safety laboratory tests ONLY at Day 4 (Visit 4);
- assessment of LTLS/CTLS.

8.6.1.6 Visit 8 (Day 8)

On Day 8, an Evaluation Visit will be performed, including the following assessments:

- record of adverse events and change in concomitant medications;
- physical evaluation and vital signs;
- KPS/LPS evaluation;
- 12 Lead ECG;
- PK blood sampling (it is a pre-dose PK sampling for patients scheduled to prolong hypouricemic treatment);
- blood sampling for safety laboratory test including centralized laboratory test (sUA);
- urine collection for safety laboratory tests;
- assessment of LTLS/CTLS.

ONLY for patients scheduled to prolong hypouricemic treatment:

- study drug administration;
- assessment of the age-appropriate formulation acceptability (only for children).

8.6.1.7 Visit 9 (Day 9)

To be performed ONLY for patients scheduled to prolong hypouricemic treatment:

- record of adverse events and change in concomitant medications;
- vital signs;
- KPS/LPS evaluation;
- study drug administration;
- assessment of the age-appropriate formulation acceptability (only for children);
- blood sampling for safety laboratory tests.

8.6.1.8 Visit 10, Follow-up/End of Study (Day 14 ± 2)

A final safety Follow-up/End of Study Visit will be performed at Day 14 (± 2):

- record of adverse events and change in concomitant medications;
- physical examination and vital signs;
- KPS/LPS evaluation;
- 12 Lead ECG;

- blood sampling and urine collection for safety laboratory tests.

8.6.2 Assessment of Pharmacokinetics/Pharmacodynamics

8.6.2.1 Pharmacokinetic parameters

Pharmacokinetic parameters will be calculated from the plasma concentration data using a limited sampling model with nonlinear mixed-effects modeling methods.

A list of parameters that can be estimated according to the PK structural model are defined in Table 2 below. Additional PK parameters may be estimated [REDACTED]

Methods for PK parameters estimation are described in section 9.3.2.

[figure not shown]
Table 2. Pharmacokinetic parameters

C_{max}	Maximum plasma concentration
T_{max}	Time to C_{max}
Vd/F	Apparent volume of distribution
CL/F	Apparent clearance
Ka	Absorption rate constant
$AUC_{(0-t)}$	The area under the plasma concentration versus time curve from time 0 to time of the last quantifiable concentration
$AUC_{(0-\tau)}$	The area under the plasma concentration versus time curve over the dosing interval, where tau is the length the dosing interval (24 hours)
$AUC_{(0-\infty)}$	The area under the plasma concentration versus time curve from time zero to infinity

8.6.2.2 Sampling and handling of blood samples for drug assays

8.6.2.2.1 Drug assay

In order to assess febuxostat pharmacokinetics following repeated dose administration in children, adolescent and adult patients, blood samples will be collected on Visits 2, 3, 4, 5, 6, 7 and 8 (i.e., after the first treatment administration and on each following visit until the Evaluation Visit). These blood samples will be drawn at trough together with the safety laboratory blood samples. Four additional blood samples are required for each patient on Visit 7 (Day 7) at the selected sampling intervals: 0.5-2 hours, 2-4 hours, 4-6 hours and 6-8 hours post study drug intake.

[figure not shown]

[figure not shown]
8.6.2.2.2 Analytical methods

The concentrations of febuxostat in plasma will be quantified using a [REDACTED] - [REDACTED] bioanalytical method by Menarini Ricerche S.p.A. (Italy). The method will be fully validated according to established Good Laboratory Practice (GLP) guidelines and international regulatory recommendations.

8.6.2.3 Centralized Laboratory Evaluation for Pharmacodynamic Parameter

At each Visit starting from Visit 1 (Day 1) until Evaluation Visit (Visit 8, Day 8), a centralized laboratory test (sUA) will be used for pharmacodynamic parameter sUA. Whenever possible, sampling will be collected in conjunction with safety laboratory tests to reduce the patient's discomfort of additional venopunctures. All samples for centralized laboratory test will be processed at the site and the serum shipped to be centrally analyzed at the Central Laboratory.

8.6.3 Assessment of Safety

8.6.3.1 Medical History

General medical history and ongoing hematological malignancy medical history will be collected at the Screening Visit in order to obtain all information necessary to confirm the inclusion of the patient in the study.

General medical history will include all the diseases (excluding the ongoing hematological malignancy) and conditions, either chronic or not, which are needed to assess inclusion/exclusion criteria and those which are relevant according to the Investigator.

The ongoing hematological malignancy medical history will include the type of tumor (i.e. lymphoma, leukemia), the date of diagnosis and the presence or absence of renal dysfunction and/or involvement.

8.6.3.2 Physical Examinations and Vital signs

A complete physical examination will be performed at Screening, Start of Treatment, Evaluation and Follow up/End of Study Visits. It includes a general appearance observation and a complete exam of the following body areas: HEENT/Neck, Lymph Nodes, Thyroid, Abdomen, Skin, Cardiovascular, Respiratory, Gastrointestinal, Neurological, Musculoskeletal/Extremities.

Vital signs will be recorded throughout the study at each visit. The following parameters will be measured:

- Heart rate (HR, beats/min);
- Blood pressure (BP, systolic and diastolic, mmHg);
- Breathing rate (BR, breaths/min);
- Body Temperature (T, °C).

8.6.3.3 Safety Laboratory Evaluation

Patient’s safety will be monitored daily at each Visit through laboratory tests. Safety laboratory assessments shall include all parameters for the evaluation of LTLS/CTLS, according to Cairo and Bishop Criteria (see Appendix I: Definition of LTLS and CTLS).

Safety tests will be locally performed in order to ensure prompt patient’s management.

The laboratory print-outs should be identified with the patient number. All print-outs should be dated and signed by the Investigator and filed in the patient’s record. The current valid version of the respective normal ranges as well as any update needs to be notified to the Sponsor. Any out of range value shall be clinically assessed by the Investigator. Safety laboratory results as well as clinical assessments for out of range values will be recorded in eCRF.

The volume of blood to be drawn for each assay will amount to a maximum of 4 ml.

Urinalysis will be performed at Screening, Visit 1, Visit 4, Visit 8 and repeated at Visit 10. Urinalysis test results shall be clinically assessed by the Investigator and the only assessments have to be recorded in eCRF.

Tests are shown in Table 3.

Table 3: Serum, Blood and Urine Sample Analyte Listing

SERUM CHEMISTRY	HEMATOLOGY	URINALYSIS
Creatinine	Haemoglobin	pH
sUA	Haematocrit	Density
Potassium	RBC count	
Phosphorus	Platelet count	
Calcium	WBC count and (absolute and %):	Nitrite
BUN / Urea	neutrophil	Protein
Albumin	lymphocyte	Glucose
Alkaline phosphatase	eosinophil	Ketones
Amylase	basophil	RBC
Glucose	monocytes	WBC
Total protein		Epithelial cells
Total bilirubin and Direct bilirubin		Casts
ALT and AST		Bacteria
LDH		Yeast
GGT		Crystals
INR		
prothrombin time/prothrombin activity		
Sodium		
Chloride		
Beta-HCG (ONLY at Screening if applicable)		
ESTIMATED PARAMETERS		
CLcr calculation according to Cockcroft and Gault formula		

In order to guarantee the proper management of the patient, any additional sampling or examination is allowed anytime, upon Investigator judgment.

8.6.3.4 12 Lead ECG

12 Lead ECG will be performed locally, using standard equipment available at site, at the following Visits: Screening Visit, Visit 3, Visit 8 and Visit 10.

Standard 12 Lead ECG will be performed at rest in supine position. All ECG print-outs should be identified with patient number, year of birth, and gender, as well as with the date and time of recording. All print-outs should be assessed, dated and signed by the Investigator and stored in the patient's record.

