6.3 RISK-BENEFIT ASSESSMENT

Febuxostat is approved in the European Union for the treatment of gout at dosages of 80 mg and 120 mg once a day, while the 120 mg strength has recently received marketing approval by the EC [8] for the prevention and treatment of hyperuricemia in adult patients undergoing chemotherapy for hematologic malignancies at intermediate to high risk of TLS. Therefore, the adult population participating to the present trial can benefit from an early access to an effective and safe treatment, whereas the pediatric population will be exposed to potential risk, which can be considered low taking into account the following evidences:

- 1) TLS is a life-threatening condition that may occur rapidly in children. Children hematologic malignancies are typically highly proliferative and highly chemosensitive. Thus, while chemotherapy may be strongly effective for them, it may also determine massive TLS with fatal outcomes. It is therefore essential to protect children with the best available and more suitable therapeutic strategy. It is worth noting that at the moment an oral age-appropriate formulation of allopurinol is not available in Europe. The present study is part of the febuxostat Pediatric Investigational Plan agreed with the Pediatric Committee of the EMA [32] and endorsed by the EMA [17].
- 2) A specific toxicology program has been run to fulfill the requirements of the febuxostat pediatric development [17]. In both adult and juvenile rats, dose-limiting toxicities were associated with obstructive nephropathies due to the precipitation of xanthine in urine. These findings are considered a consequence of species-specific purine metabolism and urine composition, and are deemed of no relevance for febuxostat clinical development. Indeed, the formation of xanthine crystals is not expected at the febuxostat dose levels recommended for adult humans and neither for children and adolescents from 6 to 17 years of age.
- 3) Febuxostat efficacy in the prevention/treatment of hyperuricemia in adult patients undergoing

chemotherapy for hematologic malignancies at intermediate to high risk of TLS was extensively proven by the FLORENCE study [30] and febuxostat 120 mg strength was recently approved for the prevention and treatment of hyperuricemia in this patient population (ADENURIC[®] SmPC Appendix II: EU SmPCs for adenuvic[®]).

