8.7.4 Management of Non-Serious Adverse Events (NSAEs) and/or laboratory abnormalities

The Investigator must record all the available information concerning any NSAE (whether or not deemed related to the investigational drug) in the corresponding section of the e-CRF, eCRF-AE pages, **within 5 calendar days** after the first knowledge of the occurrence of the event.

Once the information is saved, a notification e-mail will be automatically generated and sent to the Sponsor's DSM, so the NSAE can be retrieved

When relevant, also the CRF pages concerning medical history, concomitant medication, and laboratory test will be retrieved by the Sponsor's DSM.

Any further significant information and supporting documentation that become available (copies of laboratory, tests, procedures etc...) shall be provided by the Investigator through additional written reports to the Sponsor's DSM.

In addition, during the clinical trial, abnormalities in laboratory analyses (newly occurring after ICF signature or worsening of previously known abnormalities), which are considered clinically relevant by the Principal Investigator (values significantly above or under normal range or which require an intervention or diagnostic tests, or may result in the IMP discontinuation), should be reported as AEs. However, all abnormalities in laboratory values should be collected and reviewed by Sponsor on a bi-monthly basis.

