In patients in whom the rate of urate formation is greatly increased (e.g. malignant disease and its treatment, Lesch-Nyhan syndrome) the absolute concentration of xanthine in urine could, in rare cases, rise sufficiently to allow deposition in the urinary tract. This has not been observed in the pivotal clinical study with ADENURIC in the Tumor Lysis Syndrome. As there has been no experience with febuxostat, its use in patients with Lesch-Nyhan Syndrome is not recommended.

Mercaptopurine/azathioprine

Febuxostat use is not recommended in patients concomitantly treated with mercaptopurine/azathioprine. Where the combination cannot be avoided patients should be closely monitored. A reduction of dosage of mercaptopurine or azathioprine is recommended in order to avoid possible haematological effects (see section 4.5).

Organ transplant recipients

As there has been no experience in organ transplant recipients, the use of febuxostat in such patients is not recommended (see section 5.1).

Theophylline

Co-administration of febuxostat 80 mg and theophylline 400mg single dose in healthy subjects showed absence of any pharmacokinetic interaction (see section 4.5). Febuxostat 80 mg can be used in patients concomitantly treated with theophylline without risk of increasing theophylline plasma levels. No data is available for febuxostat 120 mg.

Liver disorders

During the combined phase 3 clinical studies, mild liver function test abnormalities were observed in patients treated with febuxostat (5.0%). Liver function test is recommended prior to the initiation of therapy with febuxostat and periodically thereafter based on clinical judgment (see section 5.1).

Thyroid disorders

Increased TSH values (>5.5 μ IU/mL) were observed in patients on long-term treatment with febuxostat (5.5%) in the long term open label extension studies. Caution is required when febuxostat is used in patients with alteration of thyroid function (see section 5.1).

Lactose

Febuxostat tablets contain lactose. Patients with rare hereditary problems of galactose intolerance, the Lapp lactase deficiency or glucose-galactose malabsorption should not take this medicine.

warfarin in healthy subjects. INR and Factor VII activity were also not affected by the co-administration of febuxostat.

Desipramine/CYP2D6 substrates

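### Section 8.6.3.3 puts only the investigator's assessment of urinalysis in the eCRF, so the frequency of crystalluria by dose and age group may not be estimable from the study database

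*Combined protocol and SAP*

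**What the plan says.** Section 8.6.3.3 sets a general rule for local safety tests: "Safety laboratory results as well as clinical assessments for out of range values will be recorded in eCRF". It then sets a different rule for urine: "Urinalysis test results shall be clinically assessed by the Investigator and the only assessments have to be recorded in eCRF". Table 3 in the same section includes crystals, RBC, protein and pH under urinalysis. Amendment No. 1 reprints that table with crystals still in it, and its listed changes do not touch the recording rule. On timing, "Urinalysis will be performed at Screening, Visit 1, Visit 4, Visit 8 and repeated at Visit 10". On source records, "All print-outs should be dated and signed by the Investigator and filed in the" patient's record.

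Section 8.7.4 makes new or worsened abnormalities reportable as adverse events if they are those "which are considered clinically relevant by the Principal Investigator". It then adds a wider duty: "all abnormalities in laboratory values should be collected and reviewed by Sponsor on a bi-monthly basis". Section 9.3.6 plans descriptive statistics for laboratory parameters by dose and age group. The laboratory safety endpoint in section 8.8.2 counts clinically significant abnormalities only.

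Sections 6.2.1 and 6.3 report that the dose-limiting toxicity in adult and juvenile rats was obstructive nephropathy from xanthine precipitating in urine. They judge this species-specific. Section 6.3 says that "the formation of xanthine crystals is not expected at the febuxostat dose levels recommended for adult humans" and extends this to ages 6 to 17. The 120 mg label in Appendix II, under Xanthine deposition, says that where urate formation is greatly increased "the absolute concentration of xanthine in urine could, in rare cases, rise sufficiently to allow deposition in the urinary tract". It gives malignant disease and its treatment as an example, and adds that this was not observed in the pivotal TLS study.

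**The concern.** The test is done and its result exists, but the protocol does not require the result in the database. What reaches the eCRF is a judgement made in an open-label trial at about 40 sites. Crystals that an investigator considers unimportant need not be visible to the sponsor's periodic review or to the safety tables.

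The item is not arbitrary. Xanthine precipitation is the animal finding that the risk-benefit section sets aside, and for ages 6 to 17 it does so as an expectation. The label's example of a setting for deposition is the setting of this trial. Section 6.3 also says that the study may help define the best paediatric dose in terms of safety as well as efficacy, and two doses are given in each paediatric age group. A count of crystal findings by dose and age group would be a natural safety summary, and the recording rule may prevent it.

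**Working it through.** The plan states no figure on this point, so there is none to reproduce. The check is a comparison of sections, followed by two calculations that give scale.

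**1. Comparison of sections**

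- Blood tests (8.6.3.3): results and assessments are entered. Urinalysis (8.6.3.3): assessments only. This is an explicit exception, not missing detail.
- Sponsor review (8.7.4): all abnormalities in laboratory values. The urinalysis rule does not require values to be entered, and no other route for them is described.
- Analysis (9.3.6): laboratory parameters summarised by dose and age group. For urinalysis only assessments would be available.
- Timing: five scheduled urinalyses, of which three (Visits 4, 8 and 10) follow the first dose. Screening and Visit 1 may fall on the same day.

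**2. What recorded results could show**

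Inputs are the planned numbers in section 8.1: 48 children and 48 adolescents, in four cohorts of about 24. For zero events in n patients, the exact two-sided 95% upper limit is 1 − 0.025^(1/n).

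- n = 24 (one cohort): 1 − 0.025^(1/24) = 14.2%
- n = 48 (one age group): 1 − 0.025^(1/48) = 7.4%
- n = 96 (all paediatric patients): 1 − 0.025^(1/96) = 3.8%

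These limits apply to crystals of any type. With significance assessments alone, zero findings in 96 would give the same 3.8%, but only for crystalluria judged clinically significant.

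**3. How much an assessment-only record could hide**

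The documents give no crystal rate and no share judged significant, so both are assumptions, shown over a range. Let p be the true proportion of patients with crystals and s the share of those patients whose finding is judged significant and so becomes visible. In 48 children the chance of at least one visible case is 1 − (1 − p·s)^48.

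| Share visible (s) | p = 2% | p = 5% | p = 10% |
|---|---|---|---|
| 100% (results recorded) | 62.1% | 91.5% | 99.4% |
| 50% | 38.3% | 70.3% | 91.5% |
| 20% | 17.5% | 38.3% | 62.1% |
| 10% | 9.2% | 21.4% | 38.3% |

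For example, at p = 5%, full recording gives 1 − 0.95^48 = 91.5%. If one finding in five is visible, the chance is 1 − 0.99^48 = 38.3%.

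**The case against.** A reader might infer that unimportant-looking crystals leave no trace, or that the trial cannot show whether xanthine crystals form in children. The documents do not support either reading.

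- Print-outs are filed at the site, and section 10.3 counts laboratory notes as source data, so results could be retrieved. This stands. The 100% source verification in section 10.4.1 does not by itself close the gap, because it checks eCRF entries against source and does not add values that the eCRF omits.
- Findings judged clinically relevant become adverse events, and section 8.7.2 puts the related tests in the eCRF. This stands.
- The rat injury was nephropathy. Creatinine and BUN/urea are safety tests whose values are entered, and creatinine enters the CTLS grading. This stands: renal harm is followed even if crystals are not counted.
- No readable objective or endpoint concerns crystalluria, and assessments can supply the endpoint as worded. This stands, but it does not remove the conflict with 8.7.4 or the lack of values for 9.3.6.
- The assessment categories on the form are not shown. If each analyte is scored as normal, abnormal but not significant, or abnormal and significant, absent and present crystals could be told apart. This stands, and it is why the conclusion says may not be estimable.
- Table 3 asks for crystals in general, so a recorded result would not identify xanthine unless type is given. This stands and limits what the fix can deliver.
- Xanthine is one of six numbered points in the risk-benefit section, and deposition was not observed in the pivotal TLS study. Both are correct. That study was in adults, so it does not settle the matter for ages 6 to 17.

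**Conclusion.** The point holds as a data-capture gap and an internal inconsistency. Section 8.6.3.3 does not require urinalysis results in the eCRF, section 8.7.4 expects all laboratory abnormalities to be collected, and section 9.3.6 would have no urinalysis values to summarise. Crystal findings judged not clinically significant can therefore stay in site records, and their frequency by dose and age group may not be estimable from the database. The rule covers all age groups, adults included.

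The documents give no crystal rate, so the size of the loss cannot be stated. Under the assumed rates and shares above it ranges from modest to large. It depends on how the assessment is coded and on how often investigators call a crystal finding significant. This is a cheap improvement to the safety data, not a flaw in the primary pharmacokinetic analysis. The stronger conclusion, that the trial is unable to detect xanthine crystals in children, does not follow: clinically relevant findings are reported, source is kept, and the test itself is not specific to xanthine.

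**What to change.** Reconcile section 8.6.3.3 with section 8.7.4. At each scheduled urinalysis, record in the eCRF the crystal result (absent or present, and type if the local laboratory reports it), RBC, protein and pH, and keep the clinical assessment beside them.

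In section 9.3.6, add a table of crystals absent or present by visit, dose and age group, with adults included, and exact 95% confidence intervals. State that the limits apply to any crystals detected, and to xanthine only where type is reported. The table is descriptive, because the paediatric dose cohorts are filled in sequence without randomisation.

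The cost is four results at up to five visits, so at most 4 × 5 = 20 entries per patient, plus crystal type where available, and one safety table. No new sample or procedure is needed. The downside is the extra data entry.
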